2.5 Data Monitoring and Other External Committees

Not applicable.

3 OBJECTIVES

3.1 Primary

- In the neoadjuvant cohort, to investigate the safety and tolerability of neoadjuvant nivolumab administration in the following tumor types:
 - HPV positive SCCHN
 - HPV negative SCCHN
 - GYN (Cervical, Vaginal, Vulvar) Carcinoma
 - Merkel Cell Carcinoma

- In the metastatic/recurrent nivolumab monotherapy cohort, to evaluate the investigator-assessed objective response rate (ORR) of nivolumab monotherapy in subjects with the following diseases:
 - Metastatic or recurrent EBV positive related Gastric cancer,
 - Metastatic or recurrent HPV positive SCCHN
 - Metastatic or recurrent GYN (Cervical, Vaginal, Vulvar) Carcinoma
 - Metastatic or recurrent Merkel Cell carcinoma
 - Metastatic or recurrent Nasopharyngeal Carcinoma (NPC)
- In the metastatic/recurrent combination therapy (nivolumab combined with either ipilimumab [Combo A or B], or BMS-986016 [Combo C]) cohort, to evaluate the investigator-assessed objective response rate (ORR) of nivolumab combination in subjects with the following diseases:
 - Metastatic or recurrent NPC
 - Metastatic or recurrent MCC
 - Metastatic or recurrent cervical cancers
 - Metastatic or recurrent HPV positive SCCHN (with primary exposure to anti-PD-1, anti-PD-L1 or anti-CTLA-4 antibody therapy [Combination C])
 - Other metastatic or recurrent anogenital HPV associated tumors (vulvar, vaginal, anal, canal, penile)
- In the metastatic cohort nivolumab combined with daratumumab (Combo D) to evaluate the investigator-assessed objective response rate (ORR) in subjects with:
 - Metastatic or recurrent HPV positive, negative, or unknown SCCHN (without prior I-O therapy exposure)

3.2 Secondary

3.2.1 Metastatic Cohorts (Monotherapy and Combination Therapy)

- To evaluate the duration of response, progression-free survival and overall survival.

3.3 Exploratory

3.3.1 Neoadjuvant Cohort

- To determine the percent change from baseline of immune cells and the percent change from baseline of select immune activation/inhibitory molecules of viral-specific T cells in tumor specific subsets of nivolumab treated subjects.
- To evaluate the recurrence-free survival after neoadjuvant administration of nivolumab and surgery
- To determine the percent change from baseline in tumor volume after two doses of neoadjuvant nivolumab.

- To determine pathologic complete response of tumors in subjects who receive surgical resection after two doses of neoadjuvant nivolumab in SCCHN, resectable Merkel Cell Carcinoma, and cervical, vaginal, or vulvar cancer.
- To evaluate changes in anti-viral and anti-tumor immune responses at the tumor site, using proliferative and/or functional assays.
- To investigate the potential association between selected biomarker measures in peripheral blood and tumor tissue, including PD-L1, with safety and clinical efficacy measures.
- To investigate the pharmacodynamic activity of nivolumab in the peripheral blood and tumor tissue as measured by gene expression, flow cytometry, immunohistochemistry and soluble factor assays.
- To study the effect of nivolumab on the viral antigen specific T cell responsiveness in the peripheral blood.
- To evaluate the potential association between the number of tumor mutations and neoantigens with clinical efficacy measures and determine if tumor antigen-specific T cells are present in the periphery.
- To assess the subject's overall health status as assessed by the EQ-5D.
- To evaluate cancer specific health related quality of life as assessed by EORTC QLQ-C30.
- To characterize pharmacokinetics of nivolumab and explore exposure-response relationships.
- To characterize the immunogenicity of nivolumab.

3.3.2 Metastatic Cohorts (Monotherapy and Combination Therapy)

- To determine the safety and tolerability [defined as toxicity rates (worst CTC grade per subject) of adverse events and specific laboratory tests] of nivolumab monotherapy and combination therapy (ipilimumab, BMS-986016, or daratumumab) in subjects with metastatic or recurrent viral-mediated tumors.
- To evaluate the pre and post treatment EBV DNA levels in subjects with EBV positive gastric cancer (monotherapy only) and nasopharyngeal carcinoma.
- To investigate the potential association between selected biomarker measures in peripheral blood and tumor tissue, including PD-L1, with safety and clinical efficacy measures.
- To investigate the pharmacodynamic activity of nivolumab monotherapy and combination therapy (ipilimumab, BMS-986016, or daratumumab) in the peripheral blood and tumor tissue as measured by gene expression, flow cytometry, immunohistochemistry and soluble factor assays.
- To study the effect of nivolumab monotherapy and combination therapy (ipilimumab, BMS-986016, or daratumumab) on the viral antigen specific T cell responsiveness in the peripheral blood.
- To evaluate the potential association between the number of tumor mutations and neoantigens with clinical efficacy measures and determine if tumor antigen-specific T cells are present in the periphery.
- To assess the subject's overall health status as assessed by the EQ-5D.
- To evaluate cancer specific health related quality of life as assessed by EORTC QLQ-C30.

- To characterize pharmacokinetics of nivolumab monotherapy and combination therapy (ipilimumab, BMS-986016, or daratumumab) and explore exposure-response relationships.
- To characterize the immunogenicity of nivolumab monotherapy and combination therapy (ipilimumab, BMS-986016, or daratumumab).

4 ENDPOINTS

4.1 Primary Endpoint

4.1.1 Neoadjuvant Cohort

- The safety and tolerability objective will be measured by the incidence of drug-related select AEs and drug-related SAEs
- Rate of surgery delay, which is defined as the proportion of subjects in the neoadjuvant cohort with surgery delayed > 4 weeks from the planned surgery date or planned start date for chemoradiation due to a drug-related AE will be reported for each tumor type.

4.1.2 Metastatic Cohorts (Monotherapy and Combination Therapies)

- The investigator-assessed objective response rate (ORR)

ORR is defined as the number of subjects with a best overall response (BOR) of confirmed complete response (CR) or partial response (PR) divided by the number of treated subjects. The BOR is defined as the best response designation, as determined by the investigator, recorded between the date of treatment assignment and the date of objectively documented progression per RECIST 1.1 or the start date of subsequent anticancer therapy, whichever occurs first. CR or PR determinations included in the BOR assessment must be confirmed by a second scan no less than 4 weeks after the criteria for response are first met. For subjects without documented progression or subsequent therapy, all available response designations will contribute to the BOR assessment. For subjects who continue treatment beyond progression, the BOR should be determined based on response designations recorded up to the time of the initial RECIST 1.1-defined progression.

4.2 Secondary Endpoints

4.2.1 Metastatic Cohorts (Monotherapy and Combination Therapies)

- Duration of response (DOR) is computed for subjects with a BOR of PR or CR and is defined as the time from first confirmed response (CR or PR) to the date of the first documented tumor progression as determined using RECIST 1.1 criteria or death due to any cause, whichever occurs first. For subjects who neither progress nor die, the DOR will be censored on the date of their last evaluable tumor assessment. The magnitude of reduction in tumor volume is defined as the percent decrease in tumor volume from baseline to nadir, observed up until the time of the first documented tumor progression or death.
- Clinical Benefit Rate (CBR) is defined as the number of participants with a best overall response (BOR) of confirmed complete response (CR) or partial response (PR) or stable disease (SD) divided by the number of treated subjects.

- Overall survival (OS) is defined as the time from first dosing date to the date of death. A subject who has not died will be censored at last known date alive.
- Investigator-assessed progression free survival (PFS) is defined as the time from first dosing date to the date of the first documented tumor progression, as determined by investigators (per RECIST 1.1), or death due to any cause. Subjects who had no baseline tumor assessment will be censored on the first dose date. Subjects who did not start subsequent anti-cancer therapy and die without a reported prior progression will be considered to have progressed on the date of their death. Subjects who did not progress or die will be censored on the date of their last tumor assessment. Subjects who did not have any on study tumor assessments and did not die will be censored on the date they were treated. Subjects who started any subsequent anti-cancer therapy without a prior reported progression will be censored at the last tumor assessment prior to or on the date of initiation of the subsequent anti-cancer therapy.

Table 4.2-1: Censoring scheme used in primary definition of PFS

Situation	Date of Progression or Censoring	Outcome
No baseline tumor assessments and no death	First Dosing date	Censored
No on study tumor assessments and no death	First Dosing date	Censored
Progression per RECIST 1.1 documented at scheduled visit or unscheduled visit and no new anticancer treatment started before	Date of the first documented tumor progression	Progressed
Subject progression free per RECIST 1.1 and no new anticancer treatment started	Date of last tumor assessment	Censored
New anticancer treatment started without a prior reported progression per RECIST 1.1 or death	Date of last tumor assessment prior or on the date of initiation of the subsequent anti-cancer therapy	Censored
Death without progression per RECIST 1.1 and no new anticancer treatment started	Date of death	Progressed

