4.3 Exploratory Endpoints

4.3.1 Neoadjuvant Cohort only

- The percent change from baseline of immune cells and the percent change from baseline of select immune activation/inhibitory molecules of viral-specific T cells in tumor specific subsets of nivolumab treated subjects will be evaluated. The percent change is the ratio of change from the baseline and baseline measurement.
- Recurrence-free survival (RFS), which is defined as the time from surgery to the date or recurrence (local, regional, metastasis, locally advanced unresectable recurrence, clinical or radiographic progression occurs after surgery) as determined by investigators, or death due to any cause, whichever occurs first. (Note: a subject who dies without reported recurrence will be considered to have recurred on the date of death.)

Table 4.3-1: Censoring scheme used in primary definition of RFS

Situation	Date of Recurrence or Censoring	Outcome
Recurrence (local, regional, metastasis, locally advanced unresectable recurrence, clinical/radiographic progression occurs after surgery)	Date of the earliest documented recurrence/progression after surgery	Event
Death without documented recurrence after surgery/biopsy	Date of death	Event
No post-surgery disease assessment and no death	Date of surgery	Censored
No recurrence and no death	Date of last evaluable disease assessment	Censored
New anticancer therapy ^a started without recurrence or death	Date of last evaluable disease assessment prior to or on the same date of initiation of subsequent therapy	Censored

^a Protocol allowed adjuvant therapy in SOC follow up phase is not counted as subsequent therapy.

Table 4.3.1-2: Censoring scheme used in sensitivity analysis of RFS

Recurrence (local, regional, metastasis, locally advanced unresectable recurrence, clinical/radiographic progression occurs after surgery)	Date of the earliest documented recurrence/progression after surgery	Event
Death without documented recurrence after surgery/biopsy	Date of death	Event
No post-surgery disease assessment and no death	Date of surgery	Censored
No recurrence and no death	Last known alive date	Censored
New anticancer therapy ^a started without recurrence or death	Date of last evaluable disease assessment prior to or on the same date of initiation of subsequent therapy	Censored

^a Protocol allowed adjuvant therapy in SOC follow up phase is not counted as subsequent therapy.

- Safety endpoints ([Section 7.6](#))

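### PFS censoring lacks the evaluable-scan condition that DOR and primary RFS carry, and the PFS text gives two rules for a death without a baseline scan

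*SAP*

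**What the plan says.** **Censoring date.** For subjects without a PFS event, the text of SAP 4.2.1 reads: "Subjects who did not progress or die will be censored on the date of their last tumor assessment". Table 4.2-1 gives "Date of last tumor assessment" for the progression-free subject. It uses the same unqualified phrase, limited to assessments up to the start of new therapy, in the subsequent-therapy row.

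For DOR, the same section says "the DOR will be censored on the date of their last evaluable tumor assessment". For RFS, Table 4.3-1 gives "Date of last evaluable disease assessment" for the subject with no recurrence and no death.

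Protocol 8.3.2 uses the unqualified phrase for both DOR and PFS. Protocol 8.3.3 defines RFS with the evaluable condition.

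**No baseline scan.** The PFS text says "Subjects who had no baseline tumor assessment will be censored on the first dose date", with no exception for death. The sentence after it sets no condition on a baseline scan and dates the event at death: "Subjects who did not start subsequent anti-cancer therapy and die without a reported prior progression will be considered to have progressed on the date of". The matching row of Table 4.2-1 is limited to "No baseline tumor assessments and no death". A separate row, "Death without progression per RECIST 1.1 and no new anticancer treatment started", is an event at the date of death. The protocol has no rule for subjects without a baseline scan. The SAP document history shows that version 2.0 revised the PFS definition on this point.

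**The concern.** Protocol Appendix 3 (Table 3.3.2-1) allows a time-point result of NE when target lesions are not all evaluated. Such a scan cannot show that the subject is free of progression. If the PFS wording is programmed as written, the interval between the last evaluable scan and an NE scan counts as progression-free follow-up. Take a responder who has taken no further therapy and whose final scan is NE. That subject's DOR would be censored at the earlier, evaluable scan and PFS at the later one, although both endpoints rest on the same progression assessments.

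The no-baseline sentence raises a different problem. A subject without a baseline scan who dies is either an event at death or censored at first dose, depending on which sentence the programmer follows. Such subjects remain in the analysis, because SAP 6.3.2 makes all treated subjects the primary efficacy population.

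What is at stake is the PFS curve and the rates at 3, 6, 9 and 12 months (SAP 7.5.2.4), in cohorts of 23 or about 40 (SAP 5).

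**Working it through.** The plan states no assumed PFS median, event count or precision, so there is no figure to reproduce. The check is of direction and rough size.

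**1. Direction of the missing evaluable condition.** At each event time the Kaplan-Meier estimate is multiplied by 1 − d/n, with d events and n at risk. Moving a censoring date later keeps that subject in the risk set at any event time between the two dates. The factor becomes 1 − d/(n + 1), which is larger. All other factors are unchanged. The curve therefore rises or stays where it is.

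**2. Size.** Inputs from the documents:
- cohort sizes 23 and 40;
- an 8-week scan interval in year 1 (Protocol Table 5.4.1-1), which is 56/30.4375 = 1.84 months by the SAP 8 conversion.

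Assumptions not in the documents:
- exponential PFS with median 4 months;
- censoring uniform between 1 and 14 months;
- 10% of censored subjects end on an NE scan, so their last evaluable scan is one interval earlier.

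There were 2,000 simulated cohorts of each size, compared at 3, 6, 9 and 12 months: 2 × 2,000 × 4 = 16,000 comparisons.
- The as-written rule never gave the lower curve (0 of 16,000).
- At 6 months it was higher by 0.53 percentage points on average. The largest single cohort differed by 15.0 points, which is the extreme of 4,000.
- The mean scales roughly with the assumed NE rate: 0.53 × 2/10 ≈ 0.1 points at 2%, and 0.53 × 5/10 ≈ 0.3 points at 5%. Rerunning the simulation at those rates agreed.

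**3. One no-baseline death in a cohort of 23.** The other 22 subjects are placed at the quantiles of the same exponential distribution, all with events. Of these, 13, 8 and 3 are event-free after 3, 6 and 12 months. Censoring the 23rd subject at first dose leaves a denominator of 22. Counting the death as an event gives 23, and the subject is in the numerator until death.

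| Handling of the 23rd subject | 3 months | 6 months | 12 months | Median (months) |
|---|---|---|---|---|
| Censored at first dose | 13/22 = 59.1% | 8/22 = 36.4% | 3/22 = 13.6% | 3.74 |
| Event, death at month 1 | 13/23 = 56.5% | 8/23 = 34.8% | 3/23 = 13.0% | 3.74 |
| Event, death at month 6 | 14/23 = 60.9% | 8/23 = 34.8% | 3/23 = 13.0% | 4.27 |
| Event, death at month 13 | 14/23 = 60.9% | 9/23 = 39.1% | 4/23 = 17.4% | 4.27 |

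Censoring at first dose discards the death, but also the event-free time before it. For a month-1 death it overstates 6-month PFS by 36.4 − 34.8 = 1.6 points. For a month-13 death it understates it by 39.1 − 36.4 = 2.7 points and lowers the median. For a month-6 death the effect is mixed.

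**The case against.** **The SAP's PFS wording follows the protocol.** Protocol 8.3.2 uses the unqualified phrase for both endpoints, so it is the SAP's DOR rule that departs from it. This is correct, and the fix should acknowledge it. It does not remove the inconsistency within the SAP.

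**The SAP never says that NE scans count.** That reading comes from a missing word, and the table row concerns subjects who are progression-free under RECIST 1.1, which an NE result does not establish. A careful programmer might apply the evaluable condition anyway. A reader might infer that the sponsor means to credit NE scans; the documents do not show that. What stands is that the date is settled for DOR and left open for PFS.

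**RFS is an imperfect comparator.** It is exploratory and neoadjuvant, and its sensitivity scheme (Table 4.3.1-2) censors subjects with no recurrence and no death at the last known alive date. The comparison holds for the primary RFS scheme only.

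**Most of the SAP already counts a no-baseline death as an event.** The PFS definition includes death from any cause, and the following sentence and Table 4.2-1 agree. A reader might infer that the text as a whole discards these deaths. It does not: one sentence is incomplete and conflicts with the rest.

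**The consequence is small.** A scan within 35 days before first dose and measurable disease are entry criteria (Protocol 3.3.1), and absence of measurable disease is a tracked deviation (SAP 7.2.2). PFS is summarised descriptively in non-comparative cohorts, with no test or threshold. This stands and limits the weight of the point.

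**Conclusion.** Wrong as written, with a small effect on a descriptive secondary endpoint.

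The missing evaluable condition can only raise the PFS curve or leave it unchanged. That result is algebraic and needs no assumption about the data. The average of 0.5 points at 6 months does rest on assumptions: the 10% NE rate, the 4-month median and the censoring pattern. Over NE rates of 2% to 10% the average runs from about 0.1 to 0.5 points, although a single small cohort can move more.

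The no-baseline sentence is an internal contradiction with few subjects behind it. A reader might infer that both wordings always flatter PFS. The calculation rules that out for the no-baseline death, where the sign depends on when the death occurs. A reader might also infer that the PFS text and Table 4.2-1 disagree on the censoring date. They agree on it; they differ only on the no-baseline death.

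**What to change.** In the PFS text of SAP 4.2.1, and in the no-event and subsequent-therapy rows of Table 4.2-1, insert *evaluable* before *tumor assessment*. State what makes an assessment evaluable, so that a time point rated NE under Appendix 3 does not qualify. Add a note that protocol 8.3.2 uses the unqualified phrase for both DOR and PFS and that the SAP refines it for both.

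In the no-baseline sentence, add the condition *and did not die*, so that it matches the Table 4.2-1 row.

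The cost is SAP wording plus a check that the PFS program follows it. No new data, sample size change or protocol amendment is needed, provided the SAP records the refinement of the protocol wording.

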4.3 Exploratory Endpoints

4.3.1 Neoadjuvant Cohort only

- The percent change from baseline of immune cells and the percent change from baseline of select immune activation/inhibitory molecules of viral-specific T cells in tumor specific subsets of nivolumab treated subjects will be evaluated. The percent change is the ratio of change from the baseline and baseline measurement.
- Recurrence-free survival (RFS), which is defined as the time from surgery to the date or recurrence (local, regional, metastasis, locally advanced unresectable recurrence, clinical or radiographic progression occurs after surgery) as determined by investigators, or death due to any cause, whichever occurs first. (Note: a subject who dies without reported recurrence will be considered to have recurred on the date of death.)

Table 4.3-1: Censoring scheme used in primary definition of RFS

Situation	Date of Recurrence or Censoring	Outcome
Recurrence (local, regional, metastasis, locally advanced unresectable recurrence, clinical/radiographic progression occurs after surgery)	Date of the earliest documented recurrence/progression after surgery	Event
Death without documented recurrence after surgery/biopsy	Date of death	Event
No post-surgery disease assessment and no death	Date of surgery	Censored
No recurrence and no death	Date of last evaluable disease assessment	Censored
New anticancer therapy ^a started without recurrence or death	Date of last evaluable disease assessment prior to or on the same date of initiation of subsequent therapy	Censored

^a Protocol allowed adjuvant therapy in SOC follow up phase is not counted as subsequent therapy.

Table 4.3.1-2: Censoring scheme used in sensitivity analysis of RFS

Recurrence (local, regional, metastasis, locally advanced unresectable recurrence, clinical/radiographic progression occurs after surgery)	Date of the earliest documented recurrence/progression after surgery	Event
Death without documented recurrence after surgery/biopsy	Date of death	Event
No post-surgery disease assessment and no death	Date of surgery	Censored
No recurrence and no death	Last known alive date	Censored
New anticancer therapy ^a started without recurrence or death	Date of last evaluable disease assessment prior to or on the same date of initiation of subsequent therapy	Censored

^a Protocol allowed adjuvant therapy in SOC follow up phase is not counted as subsequent therapy.

- Safety endpoints ([Section 7.6](#))
- The percent change in tumor volume from baseline after two doses of neoadjuvant nivolumab is defined as the ratio of the change in tumor volume and the baseline tumor volume.
- The proportion of treated subjects who experiences pathologic complete response will be used to determine pathologic response rate of tumors after two doses of neoadjuvant nivolumab in HPV positive and negative SCCHN, resectable Merkel Cell Carcinoma, and HPV positive

cervical, vaginal, or vulvar cancer. Pathological complete response (pCR) is defined as the absence of residual invasive cancer on hematoxylin and eosin evaluation of the complete resected tumor specimen and all sampled regional lymph nodes following completion of neoadjuvant systemic therapy.

